**Clinical activity:**

In the dose expansion phase, we will quantify best IWG response at any time, clinical parameters such as weekly transfusion requirements after each cycle of therapy compared to baseline, blood

counts after each cycle compared to baseline, quality of life (QOL) assessment per the FACTleu questionnaire at the completion of the induction and maintenance phases compared to baseline, time from treatment initiation to disease progression, and time to death. We will also assess for best IWG response at any time and HI in our AML patients per the IWG-2006 MDS criteria (Appendix A3). We will look at all clinical parameters both in aggregate and as a subgroup analysis in AML and MDS patients. For response calculations, the report will contain at least a section with all eligible patients. Another section of the report will detail the response rate for evaluable patients only. The response rate analysis based on a subset of patients will explain which patients were excluded and for what reasons. We will provide 95% confidence limits as appropriate. Average weekly transfusion requirements over the duration of a 28-day cycle will be compared to the baseline average weekly transfusion requirement over the 4 to 8 weeks prior to treatment initiation. Event free survival (EFS) and overall survival (OS) will be reported with a 95% confidence interval.

FACTleu version 4 questionnaires will be analyzed per instructions on FACIT.org (Cella et al., 2012). Scoring guidelines are listed in Appendix D. We hypothesize that QOL will improve over the course of the study; however, without a comparison arm, it will be difficult to determine whether this regimen will yield a better or worse QOL outcome than other regimens. Therefore, the questionnaire will serve as more of an exploratory assessment to use when planning further studies. We will look at markers of feasibility, including percentage of completed questions, the time it takes to complete, and how many patients participate in the survey.

### **Toxicity:**

Beyond the dose escalation portion of the study, we will continue to track for adverse events throughout the duration of the trial. We will evaluate the number of patients who experience different toxicities with percentages and descriptive statistics and will explore any potential correlations between IRX5183-induced differentiation, toxicity, and clinical responses (e.g. whether patients who experience toxicities characteristic of DS have a higher chance of clinical response). Therefore, IWG responses and survival endpoints will be qualitatively compared between patients who do and do not have evidence of DS, if we do happen to see this clinical syndrome in our study population.

### **Exploratory assessments:**

We plan to assess whether observed *in vivo* evidence of differentiation per flow cytometry markers, ANC, or BM blast count correlate with ORR, EFS, and/or OS.

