## 1. OBJECTIVES

### HYPOTHESIS:

We hypothesize that the administration of IRX5183 to patients with relapsed/refractory acute myeloid leukemia (R/R-AML) and high-risk myelodysplastic syndrome (HR-MDS) will be well tolerated and share a similar toxicity profile of adverse events (AEs) to all-trans retinoic acid (ATRA). We hypothesize that the net clinical effect of IRX5183 administration in patients with R/R-AML and HR-MDS will be a measurable improvement in hematologic parameters and/or a reduction in bone marrow (BM) blast numbers. We predict that IRX5183 administration and consequent differentiation and apoptosis of leukemia cells will lead to measurable laboratory parameters of differentiation and these will correlate with clinical responses and toxic events.

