### **7.3. Measurement of Response / Response Criteria:**

The primary endpoint of clinical response is defined by the International Working Group recommendations (see Appendix A1-A3) for therapeutic trials in AML and MDS and includes CR, complete remission with incomplete count recovery (CRi, formerly known as morphologic leukemia-free state or marrow CR), partial remission (PR), HI, SD, and PD (Cheson et al., 2003). We will also include an assessment of HI per MDS IWG-2006 recommendations as one of our secondary endpoints in our AML patients (see Appendix A2). In addition to the criteria in Appendix A1, the following will be considered as PD:

- 1) A significant increase in bone marrow blasts beyond 4 weeks of starting the drug:
  - a. if baseline 51-100% blasts – an increase of greater than 50% of baseline
  - b. if baseline 26-50% blasts – an increase up to 2 x the baseline
  - c. if baseline 0-25% blasts – an increase up to 3 x the baseline
- 2) A rising peripheral WBC after adequate dosing with hydroxyurea (see section 5.3 above)

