## 11. STATISTICAL CONSIDERATIONS

### 11.1. Study design & endpoints:

In the dose-escalation part of the study, there will be 3 dose levels (dose level 1 [DL1] with 50 mg, DL2 with 75 mg, and DL3 with 100 mg), with 1 additional dose level to be only used if excessive toxicity noted at the DL1. There will be no intra-patient dose escalation. Dose-escalation rules are defined through a standard 3+3 algorithm as outlined in Section 5.2.

The phase II expansion part of the study will aim to recruit a total of 27 patients with either R/R-AML or HR-MDS, and there will be an interim analysis after 13 patients for futility through a Simon two-stage minimax design based upon a Type I error rate of 0.05, power of 0.8, response probability of poor drug 0.05, and response probability of good drug of 0.2, based on prior relapsed and refractory AML trials and CTEP data on non-pediatric oncology trials from 2001 to 2012 (Itzykson et al., 2015; Ritchie et al., 2013; Thol et al., 2015; Yoko Korenaga Fukuda, 2014). Stage 1 will enroll 13 patients at the RP2D and will require at least 1 response for

continued enrollment to Stage 2, to reach the total of 27 patients. A total of 4 or more responses out of 27 patients will be considered encouraging evidence for future larger clinical trials of IRX5183.

Response will be defined per IWG criteria as CR, CRi, or PR for AML patients and as CR, CRi, PR, or HI for MDS patients (see definitions in Appendix A) and will be determined with each BM assessment. The composite of these responses across our study population will be referred to as the overall response rate (ORR). Rates of CR, CRi, PR, HI, and the composite endpoint of ORR will be summarized and reported with an exact 95% confidence interval.

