**Pharmacodynamics:**

Biologic correlates include measurement of markers of myeloid differentiation by flow cytometry (e.g. CD15, CD11b), BM blast count, and ANC at the different dose levels in the dose escalation phase and at the RP2D in the expansion phase at the different time points compared to baseline. In addition, we will look at the ratio of ANC to BM blast count as clinical marker for differentiation at the different time points compared to baseline. Statistics will be descriptive and will consist of paired Student's t-tests or Wilcoxon rank sum tests comparing averages between 2 time points (e.g. after induction therapy compared to baseline).

We will furthermore assess *in vivo* changes in detectable chromosomal abnormalities in patients with baseline cytogenetic alterations that define their malignant clones. This will be measured by fluorescent in situ hybridization (FISH) with cells from the individual cellular compartments quantified as a ratio of malignant to non-malignant cells (i.e., mononuclear cells with the cytogenetic finding to those without). Successful differentiation would be expected to result in a decrease in mononuclear cells harboring the cytogenetic abnormality. These results will be summarized using descriptive statistics and exploratory plots will be used to illustrate results.

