**APPENDIX A1.** Modified International Working Group (IWG)-2003 (A) response criteria, (B) treatment failure, and (C) endpoints in AML.

**A.**

Response Criterion	Time of Assessment	Neutrophils (μL)	Platelets (μL)	Bone Marrow Blasts (%)	Other
Early treatment assessment	7-10 days after therapy	NA	NA	< 5	
Morphologic leukemia-free state	Varies by protocol	NA	NA	< 5	Flow cytometry EMD
Morphologic CR	Varies by protocol	> 1,000	> 100,000	< 5	Transfusion EMD
Cytogenetic CR	Varies by protocol	> 1,000	> 100,000	< 5	Cyogenetics—normal, EMD
Molecular CR	Varies by protocol	> 1,000	> 100,000	< 5	Molecular—negative, EMD
Partial remission	Varies by protocol	> 1,000	> 100,000	> 50 or decrease to 5-25	Blasts < 5% if Auer rod positive

Abbreviations: AML, acute myelogenous leukemia; EMD, extramedullary disease; CR, complete remission.

**B.**

Category	Definition
Resistant disease	Patient survives $\geq$ 7 days post-CT; persistent AML in blood or bone marrow
Aplasia	Patient survives $\geq$ 7 days post-CT; death while cytopenic, with aplastic bone marrow
Indeterminate cause	Patients who die < 7 days posttherapy Patients who die > 7 days posttherapy with no PB blasts, but no bone marrow examination Patients who do not complete the first course of therapy
Morphologic relapse	Reappearance of blasts post-CR in PB or bone marrow
Molecular or cytogenetic relapse	Reappearance of molecular or cytogenetic abnormality

Abbreviations: AML, acute myelogenous leukemia; CT, chemotherapy; PB, peripheral blood; CR, complete remission.

**C.**

Outcome	Response Category	Point of Measurement	Definition
Overall survival	All patients	Entry onto trial	Death from any cause
Relapse-free survival	CR	Leukemia-free state	Disease relapse or patient death from any cause
Event-free survival	All patients*	Entry onto trial	Treatment failure, disease relapse, or patient death from any cause
Remission duration	CR	Date of CR	Disease relapse

NOTE. Complete blood counts should be evaluated at least monthly, or more often if clinically indicated, to establish the durability of responses. Abbreviations: AML, acute myelogenous leukemia; CR, complete remission.

\*Under circumstances where presentation of event-free survival may be appropriate for responders only, this point should be clearly stated.

(Cheson et al., 2003)

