**APPENDIX A2. Modified International Working Group (IWG)-2006 response criteria for altering natural history of MDS.**

Category	Response criteria (responses must last at least 4 wk)
Complete remission	
Bone marrow: <math>\leq 5\%</math> myeloblasts with normal maturation of all cell lines*
 
Persistent dysplasia will be noted**†
 
Peripheral blood‡
 
Hgb <math>\geq 11</math> g/dL
 
Platelets <math>\geq 100 \times 10^9/L</math>
 
Neutrophils <math>\geq 1.0 \times 10^9/L</math>†
 
Blasts 0%

Partial Remission	
All CR criteria if abnormal before treatment except:
 
Bone marrow blasts decreased by <math>\geq 50\%</math> over pretreatment but still <math>> 5\%</math>
 
Cellularity and morphology not relevant

Marrow CR†	
Bone marrow: <math>\leq 5\%</math> myeloblasts and decrease by <math>\geq 50\%</math> over pretreatment†
 
Peripheral blood: if HI responses, they will be noted in addition to marrow CR†

Stable disease	Failure to achieve at least PR, but no evidence of progression for $> 8$ wks
Failure	Death during treatment or disease progression characterized by worsening of cytopenias, increase in percentage of bone marrow blasts, or progression to a more advanced MDS FAB subtype than pretreatment
Relapse after CR or PR	
At least 1 of the following:
 
Return to pretreatment bone marrow blast percentage
 
Decrement of <math>\geq 50\%</math> from maximum remission/response levels in <math>\square</math>granulocytes or platelets
 
Reduction in Hgb concentration by <math>\geq 1.5</math> g/dL or transfusion dependence

Cytogenetic response	
Complete
 
Disappearance of the chromosomal abnormality without appearance of new ones
 
Partial
 
At least 50% reduction of the chromosomal abnormality
 
For patients with:

Disease progression	
Less than 5% blasts: <math>\geq 50\%</math> increase in blasts to <math>> 5\%</math> blasts
 
5%-10% blasts: <math>\geq 50\%</math> increase to <math>> 10\%</math> blasts
 
10%-20% blasts: <math>\geq 50\%</math> increase to <math>> 20\%</math> blasts
 
20%-30% blasts: <math>\geq 50\%</math> increase to <math>> 30\%</math> blasts
 
Any of the following:
 
At least 50% decrement from maximum remission/response in granulocytes or platelets
 
Reduction in Hgb by <math>\geq 2</math> g/dL
 
Transfusion dependency <math>\square</math>

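### The planned correlation of ANC and marrow blast count with ORR is partly built in, because ORR is largely defined by those same measurements

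*Combined protocol and SAP*

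**What the plan says.** - **Exploratory assessments (section 11.7).** The plan will examine whether in vivo "evidence of differentiation per flow cytometry markers, ANC, or BM blast count correlate with ORR, EFS, and/or OS". It names no statistic, cut-off, significance level or time point.
- **Pharmacodynamics (section 11.7).** ANC and marrow blast count are compared with baseline at several time points, and the plan adds the "ratio of ANC to BM blast count as clinical marker for differentiation". Its example of a comparison is the reading after induction against baseline.
- **ORR (section 11.1).** "Response will be defined per IWG criteria as CR, CRi, or PR for AML patients and as CR, CRi, PR, or HI for MDS patients". Section 7.3 describes CRi as "formerly known as morphologic leukemia-free state or marrow CR".
- **Hypothesis (section 1, and the synopsis).** The drug is expected to produce measurable laboratory parameters of differentiation, and "these will correlate with clinical responses and toxic events".

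**The concern.** When a marker is also an ingredient of the outcome, the two are associated before any biology enters. A patient with AML reaches CR, CRi or PR only if marrow blasts fall. If a blast fall is also counted as evidence of differentiation, responders will tend to show it whatever caused it: differentiation, cytoreduction (section 5.3.2 allows hydroxyurea on treatment), or variation between marrow samples.

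The protocol itself treats blasts as an ambiguous marker of differentiation. Section 5.6 says that a rise in blasts may reflect differentiation, yet only a fall can yield CR, CRi or PR.

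At stake is the mechanistic reading of the trial. The link between differentiation and response is part of the stated hypothesis, and section 8.1 regards biologic activity as critical to interpreting clinical activity. A correlation that is partly definitional could be reported as support for that link.

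**Working it through.** **1. Marker and outcome side by side** (Appendices A1 to A3, sections 7.3 and 11.1)

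| Response component | Marrow blasts in definition | ANC in definition |
|---|---|---|
| AML CR | below 5% | above 1,000/µL |
| AML CRi (leukemia-free state) | below 5% | not applicable |
| AML PR | decrease to 5-25% | above 1,000/µL |
| MDS CR | at most 5% | at least 1.0 x 10^9/L |
| MDS marrow CR | at most 5% and at least a 50% fall | none |
| MDS PR | at least a 50% fall, still above 5% | CR count criteria, if abnormal before treatment |
| HI, neutrophil | none | at least a 100% rise, and more than 0.5 x 10^9/L |
| HI, erythroid or platelet | none | none |

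Blasts enter every AML response and every MDS response except HI. ANC enters fewer components. Erythroid or platelet HI involves neither.

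**2. Timing.** Section 5.1 makes the marrow after cycle 2, the end of induction, the primary response assessment. The pharmacodynamic example uses the post-induction reading. The plan therefore permits one marrow to supply both marker and outcome.

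**3. The plan's design, reproduced.** Inputs from section 11.1: p0 = 0.05, p1 = 0.20, 13 patients in stage 1, continue with at least 1 response, success with at least 4 of 27.
- Exact type I error, P(X1 ≥ 1 and X1 + X2 ≥ 4) at p = 0.05: 0.0416.
- Exact power, the same event at p = 0.20: 0.801. The stated 0.05 and 0.8 are met.

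**4. How often an inactive drug gives a correlation to compute** (p = 0.05)
- Stop at stage 1 with no responder: 0.95^13 = 0.513.
- Expected responders among 27, ignoring the stop: 27 x 0.05 = 1.35.
- Reach stage 2 with exactly one responder: 13 x 0.05 x 0.95^12 x 0.95^14 = 0.171.
- Reach stage 2 with at least two: 1 - 0.513 - 0.171 = 0.32 (rounded). With at least three: 0.14.
- With one responder of 27, the smallest two-sided exact rank p-value is 2/27 = 0.074, so nominal significance is impossible.

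**5. Size of the built-in association under an inactive drug.** In the simulation, 4,000 trials per scenario, baseline and follow-up blasts, ANC, platelets and hemoglobin differ only by noise. Response follows simplified appendix thresholds without the durability rules, and the stage 1 stop is applied. The documents give no noise level or case mix, so these are assumptions: AML share 50-100%, log-scale SD 0.4-1.0, and HI counted either in all lineages or in neutrophils only. Scenarios with a null ORR of 3-7%, around the plan's 5%, were kept. Responders and non-responders were compared by an exact Mann-Whitney test, which is the simulation's choice and not the plan's.

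| Scenario | Null ORR | AUC, blast fall | AUC, ANC rise | AUC, independent marker | p < 0.05: blast / ANC / independent* |
|---|---|---|---|---|---|
| All AML, SD 1.0 | 3.5% | 0.95 | 0.62 | 0.50 | 40% / 3% / 2% |
| 75% AML, neutrophil HI only, SD 0.8 | 6.8% | 0.77 | 0.67 | 0.50 | 31% / 14% / 3% |
| 50% AML, neutrophil HI only, SD 0.6 | 6.3% | 0.77 | 0.70 | 0.50 | 28% / 18% / 4% |

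*Among trials that pass stage 1 and so have at least one responder.

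Over all retained scenarios, mean AUC was 0.55-0.95 for blast fall and 0.56-0.70 for ANC rise. The low ends come from scenarios where erythroid and platelet HI also count. At least one of blast fall, ANC rise and their ratio reached p < 0.05 in 9-54% of trials with a responder, and in 3-31% of all trials.

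**6. If the drug is active.** At 20% response by any mechanism, P(0 of 13) = 0.8^13 = 0.055, and about 27 x 0.20 = 5.4 of 27 respond. The correlation is then usually computable, and the overlap remains.

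**The case against.** A reader might infer that the correlation will confirm the hypothesis even if the drug does nothing. The documents do not support that. At the plan's null rate the trial stops with no responder about 51% of the time, and a nominally significant result in 3-31% of all null trials is inflated but far from certain. A model that defines response by blasts below 5% alone, restricted to samples of 27 with at least two responders, gives nominal significance for blast fall in 87-92% of samples. It leaves out PR, HI and the stage 1 stop, so it does not describe this trial.

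A reader might also infer that no patient can respond without the marker moving. Erythroid or platelet HI in MDS needs neither a blast nor an ANC change, and AML CRi needs no ANC change.

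Other points against stand as well:
- The analysis is one sentence, labelled exploratory, with no test or decision attached. Encouragement for larger trials is tied to 4 or more responses in 27.
- The same sentence covers flow markers and OS, which are not defined by blasts or ANC. Section 8.1 lists further differentiation readouts.
- The ANC-to-blast ratio appears only as a descriptive change from baseline. The exploratory sentence does not list it for correlation with ORR.
- MDS responses must last 4 weeks, or 8 weeks for HI, which limits the part played by random variation. The simulation omits this.
- The 0.50 for an independent marker is a modelling reference. It does not show that CD11b or CD15 is independent of response.

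These points limit the size and consequence. They do not remove the overlap of blasts and ANC with ORR, or the missing time point.

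**Conclusion.** The concern holds in a limited form. As worded, the correlation of marrow blasts and ANC with ORR is biased toward supporting the hypothesis and cannot distinguish differentiation from other causes of a blast fall. The overlap is strongest for blasts in AML, weaker for ANC, and diluted in MDS by erythroid or platelet HI. For EFS it is partial, because treatment failure in Appendices A1 and A2 includes persistent AML or rising blasts.

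The existence and direction of the bias follow from the definitions, and the direction was the same in every simulated scenario. Its size is not fixed by the documents and rests on the assumed noise and case mix. The practical risk is greatest if the drug produces responses, since the correlation is then usually computable. The wording should be corrected, but the primary analysis does not depend on it.

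**What to change.** Amend the Exploratory assessments paragraph of section 11.7 as follows.

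1. Limit the correlation with ORR to markers outside the response definition: CD11b/CD15 by flow, mature neutrophils carrying the malignant abnormality by FISH, the plasma NB4 assay, and the LSC/HSC ratio where available.
2. Fix the reading at day 14 (± 3 days) of cycle 1, or after cycle 1 if there is no day-14 marrow. Both precede the primary response assessment after cycle 2.
3. Report ANC, marrow blasts and their ratio only as descriptive changes from baseline.
4. If ANC or blasts are related to EFS or OS, use a landmark analysis: start follow-up at the marker reading and include only patients still event-free (EFS) or alive (OS) at that time.
5. State how many patients contribute to each marker.

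The assays are already planned in section 8.1, so the change needs no new patients and no new assay. The cost is smaller numbers. Section 7.2 does not require the day-14 marrow for staying on study, FISH applies only to patients with a suitable baseline abnormality, and the LSC/HSC ratio depends on disease phenotype, with later readings only in select patients. With few responders these correlations will be imprecise and should be presented so.

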## **11.8. Reporting and exclusions:**

### **11.8.1. Evaluation of toxicity:**

All patients will be evaluable for toxicity from the time of their first treatment with IRX5183.

### **11.8.2. Evaluation of response:**

All patients included in the study that complete 2 cycles of therapy will be assessed for response to treatment, even if there are major protocol treatment deviations or if they are ineligible. The primary endpoint to the dose expansion phase is response per IWG criteria after receiving at least 2 cycles of therapy. Only those patients who have measurable disease present at baseline, have received at least 2 cycles of therapy, and have had their disease re-evaluated will be considered evaluable for response. These patients will have their response classified according to the definitions stated in Appendix A. Patients who exhibit objective disease progression prior to the end of cycle 2 will be considered not evaluable and will be taken off study.

An incorrect treatment schedule or drug administration does not result in exclusion from the analysis of the response rate. Patients with disease progression, death due to their disease, and death due to toxicity prior to completion of induction therapy will be excluded from the primary analysis. This will prevent dismissal of an active drug based on progression in patients with highly refractory disease who are unable to receive enough of the drug to see a clinical benefit. Patients who are unable to complete induction therapy for any reason will be treated as missing data and additional patients will be recruited in their place to reach our target sample size of 27 for phase II.

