**Study Phase II:**

The phase II part of the study will use the optimal dose identified in the phase I part of the study and will aim to recruit a total of 27 patients with AML and HR-MDS at the RP2D (see sample size calculation in section 11). The primary goal of the therapy in this phase of the trial is to determine response after receiving at least 2 cycles of therapy per IWG criteria. Analysis of clinical response will take place after the first 13 patients complete induction therapy, and enrollment will continue to the planned 27 patients if the first stage has at least 1 patient achieve a CR or CRi or PR (AML) or CR or PR or HI (MDS). We will halt enrollment after the first 13 patients complete induction therapy until we have their response data. In addition to IWG response, many secondary endpoints will be assessed as outlined in section 11 below.

**Figure 2: IRX5183 Administration Schema.** Induction phase will consist of 56 days of oral IRX5183 daily. Consolidation/maintenance phase will begin once patient has confirmed SD or better and will continue for up to four 28-day cycles. If patient is in CR after consolidation/maintenance, will hold therapy and monitor, and resume therapy if they relapse. If they have SD or better after consolidation/maintenance, they will continue on maintenance therapy for up to 1 additional year. Select patients may be eligible to continue for longer.

**Table 1: Dose Escalation of oral IRX5183 administration in phase I part of the study.** \*: DL(-1) will only recruit if the maximally

administered dose was reached at DL1. DL: dose level.

Dose level (DL)	Daily dose (mg)
DL(-1)*	25
DL1	50
DL2	75
DL3	100

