### **11.2. Primary endpoints:**

1) Phase I - description of toxicity of IRX5183 by grading and tabulation using NCI-CTC Version 4.0 criteria (section 8). The DLT will be defined as per section 5.2.

2) Phase II – best response after at least 2 cycles of therapy per IWG criteria (**Appendix A**).

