### **11.4. Sample size considerations:**

For the dose-escalation part of the trial, we will enroll up to 18 patients, per standard 3+3 design with 3 DLs (see table 2 in section 5.2). Once we have determined our RP2D, we will proceed to phase II of the trial, where we will recruit an additional 21 R/R-AML or HR-MDS patients at the RP2D, for a total sample size at the RP2D of 27 (inclusive of patients treated at the RP2D in phase I). This sample size was determined using a minimax Simon two-stage design, as described in Section 11.1. Based on prior experience at our institution in this patient population, we will account for a dropout rate of 30%, so we will aim to recruit an additional 8 patients to the dose expansion phase, so that our trial will accrue up to 35 patients to this phase.

In phase II of the trial, the study team will meet regularly to determine whether it is worthwhile to continue enrollment, if an excessive number of patients are unable to complete 2 full cycles of therapy at the RP2D, whether for reasons of DLTs or PD.

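### Both Simon cut-offs count only patients who complete 2 cycles, but the benchmark rates and the conclusion are not tied to completers, and accrual of 35 is too small for 27 completers at the plan's own 30% dropout

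*Combined protocol and SAP*

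**What the plan says.** - **Endpoint.** Section 11.2 defines the phase II primary endpoint as "best response after at least 2 cycles of therapy per IWG criteria".
- **Design.** Section 11.1 gives a Simon minimax design with type I error 0.05, power 0.8 and "response probability of poor drug 0.05, and response probability of good drug of 0.2, based on prior relapsed and refractory AML trials". It also cites pooled CTEP trial data. It requires at least 1 response in stage 1 (13 patients) and states that "A total of 4 or more responses out of 27 patients will be considered encouraging evidence".
- **Who is counted.** Section 5.1 (Study Phase II) says "Analysis of clinical response will take place after the first 13 patients complete induction therapy". Section 11.8.2 excludes early progression and disease death from the primary analysis, and likewise "death due to toxicity prior to completion of induction therapy will be excluded from the primary analysis". Anyone else who does not finish induction is treated as missing, and "additional patients will be recruited in their place to reach our target sample size of 27 for phase II".
- **Accrual.** Section 11.4 says "Based on prior experience at our institution in this patient population, we will account for a dropout rate of 30" per cent. It adds 8 patients, "so that our trial will accrue up to 35 patients to this phase". The target of 27 includes phase I patients treated at the recommended phase 2 dose (RP2D), with 21 new patients, so six carried over. The same section has the study team meet regularly to consider whether to go on if too many patients cannot complete 2 cycles.
- **Reporting.** Section 11.7 (Clinical activity) requires one response section for all eligible patients and another for evaluable patients, with reasons for exclusion.

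**The concern.** Section 11.1 speaks of enrolling 13 patients in stage 1, but Sections 5.1 and 11.8.2 make both counts completer counts. Early failures leave the denominator and are replaced. That is a legitimate choice if the benchmark rates and the conclusion use the same population, but Section 11.1 says so for neither. A reader could take 4 of 27 as a response rate for all patients given IRX5183 at the RP2D.

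The two rates can differ widely. In the group's two earlier differentiation trials (Section 2.3), 13 of 26 and 10 of 24 treated patients completed 2 cycles, and the response rates quoted there are completer rates.

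Separately, the allowance for dropout multiplies where it should divide. Replacement up to 27 therefore conflicts with a ceiling of 35. The plan also does not say how the cut-off is read if accrual ends below 27 completers with 3 or fewer responses. That reading would then be settled after the data are seen.

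**Working it through.** **1. Reproduce the design.** Inputs (Section 11.1): n1 = 13, continue with ≥1 response; n = 27, favourable with ≥4; p0 = 0.05, p1 = 0.20.

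P(favourable | p) = Σ over x = 1 to 13 of P[Bin(13, p) = x] × P[Bin(14, p) ≥ 4 − x].

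- p = 0.05: 0.0416
- p = 0.20: 0.8011

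The stated design is correct when all 27 counted patients are assessed.

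**2. Reproduce the accrual figure.** Section 11.4: 27 × 0.30 = 8.1, and 27 + 8 = 35. But if 30% of treated patients drop out, 27 completers need 27/(1 − 0.30) = 38.6, about 39 treated. From 35 treated, expected completers are 35 × 0.70 = 24.5.

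**3. Chance of 27 completers at 70% completion.** The text does not settle whether the 35 includes the six phase I RP2D patients: 27 + 8 = 35 and the 27 includes them, yet the 35 are accrued to the expansion phase.

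| Reading | Calculation | Chance |
|---|---|---|
| 35 includes phase I patients | P[Bin(35, 0.7) ≥ 27] | 23% |
| same, all six phase I patients completed | P[Bin(29, 0.7) ≥ 21] | 48% |
| six are additional (41 treated) | P[Bin(41, 0.7) ≥ 27] | 78% |
| same, all six completed | P[Bin(35, 0.7) ≥ 21] | 93% |
| 39 treated in all | P[Bin(39, 0.7) ≥ 27] | 62% |
| 42 treated in all | P[Bin(42, 0.7) ≥ 27] | 84% |

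**4. Power at a fixed ceiling.** Assume a 20% response rate in completers, 30% dropout, the stage 1 look at 13 completers, and 4 responses sufficient even below 27 completers. Power is the average of the two-stage power over the number of completers C, capped at 27. With the cut-off kept at 4, the two-stage power is 0.727 at 24 completers, 0.755 at 25, 0.779 at 26 and 0.801 at 27.

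- 35 treated: power 0.727, type I error 0.031
- 41 treated: power 0.788, type I error 0.039

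**5. How far the denominator can matter.** Section 2.3 reports 5/13 = 38% and 6/10 = 60% among completers. Over all treated patients these would be 5/26 = 19% and 6/24 = 25%, if no non-completer responded. Completion was 23/50 = 46%. Those trials used other drug combinations, so this is a guide only.

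**6. Conditional check on type I error.** Suppose p0 = 5% were an all-treated rate and every dropout a non-responder. The null rate among completers is then 0.05/0.70 = 0.0714, and the formula in step 1 gives 0.118 with full replacement to 27. If dropout is unrelated to response, there is no inflation.

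**The case against.** **The completer denominator is pre-specified and reasoned.** Section 11.8.2 explains that an active drug should not be dismissed because patients with highly refractory disease could not take enough of it. The endpoint wording also points to a completer rate. This stands, and no change of primary denominator is called for. The reason given does not, however, cover toxic deaths, although these still count for safety (Sections 7.1 and 11.8.1).

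**Early failures are already classed and reported.** Appendix A2 counts death on treatment and progression as failure. Part B of Appendix A1 puts patients who do not finish the first course under treatment failure. Section 11.7 plans an all-eligible response section. This largely stands. But that section is not tied to either decision point, and other withdrawals are not clearly placed.

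**A shortfall is not ignored.** Section 11.8.2 replaces patients up to 27, and Section 11.4 has the team review. Both are fair points, but the first conflicts with the ceiling of 35, and the second is discretionary with no threshold.

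**Stronger readings that the documents do not support.**

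- A reader might infer that false-positive error is inflated to 11.8%. That needs p0 to be an all-treated rate. The documents do not give the denominators of the source rates, and the endpoint wording argues against it.
- A reader might infer that the trial fails unless 27 completers are reached, so that power collapses. The cut-off is a count of responses: once 4 are seen, later completers cannot undo them.
- A reader might infer that 46% completion in the earlier trials disproves the 30% dropout figure. Those were different regimens, and the 30% rests on wider institutional experience.

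**Conclusion.** The point holds as a should-fix. The accrual figure is too low on the plan's own input: 35 treated gives 24.5 expected completers against a target of 27. If the 35 includes phase I patients, the chance of reaching 27 is 23% (48% if all six phase I patients completed) and power is about 0.73, not 0.80. If six are additional, the chance is 78% (93% if all six completed) and power is about 0.79 at 41 treated. The loss is therefore modest to small, depending on a reading that the plan leaves open.

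Taking the benchmark rates as completer rates, type I error stays at or below 4.2% and the conclusion covers completers only. Error of up to 11.8% at 30% dropout remains a conditional possibility until the source denominators are checked.

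The completion figures assume that patients drop out independently at 30%. The power figures also assume a 20% response rate among completers and that 4 responses suffice below 27.

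**What to change.** 1. **Section 11.4.** Restate accrual as about 39 treated (27 completers on average) or 42 (84% chance of 27). Alternatively, keep 35 and state its expected yield (24.5 completers) and power (about 0.73). Say whether the figure includes phase I RP2D patients, and reconcile it with replacement to 27.
2. **Sections 11.1 and 11.8.2.** Check the denominators of the source rates. Then state that p0, p1, type I error and power refer to patients who complete 2 cycles, and limit the favourable conclusion to them. If the sources used all treated patients, p0 and p1 need restating for completers; relabelling them would hide the mismatch.
3. **Beside each decision, at stage 1 and at the end.** Report the response rate with exact 95% confidence interval in all patients dosed at the RP2D. Count progression or death before the cycle-2 assessment as non-response, in line with Appendix A. Say how other withdrawals are classed, and list the number replaced by reason. This extends the all-eligible section in 11.7.
4. **Shortfall.** State that 4 responses meet the rule even with fewer than 27 completers, and how an ending below 27 with 3 or fewer responses is read.

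**Cost.** A few sentences in 5.1, 11.1, 11.4 and 11.8.2 and one table row, with no loss of power. Keeping 35 adds no patients. Raising accrual to 39–42 adds 4–7 patients, about 1.3 to 2.3 months at the maximum rate of 3 a month in Section 11.5.
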